#### ***4.7. Graphical Displays***

In addition to the tables and listings described above, the following graphical displays will also be included for in HIV-1 infected subjects:

- Mean (+/- Standard Error [SE]) viral load levels ( $\log_{10}$  copies/mL) at all scheduled visits;
- Mean (+/- SE) change from Baseline in viral load levels ( $\log 10$  copies/mL) at all scheduled visits;
- Mean (+/- SE) CD4+ cell count (cells/mm^3) at all scheduled visits; and
- Mean (+/- SE) change from Baseline in CD4+ T-cell count (cells/mm^3) at all scheduled visits.

#### **4.8. Exploratory/Other Analyses**

Exploratory statistical analyses will examine any noted changes in HIV-1 drug sensitivity/susceptibility in participants with an increase in plasma viral load to levels above 1,000 copies/mL on two consecutive measurements at least 2 weeks apart. These reports will be prepared separately from the report prepared in accordance with the rest of this SAP.

## Addendum

Protocol v7.0 (Amendment 6) for the TMB-302 study includes the following update that affects the analysis of the data:

Note: HIV-infected subjects who are enrolled in the IM injection study and are unable to adhere to the study schedule for IM dosing due to factors outside the study will be discontinued. Re-enrollment of HIV-infected IM Group subjects will be allowed after a Discontinuation Visit and Screening Visit are completed provided that inclusion/exclusion criteria continue to be satisfied and dosing after discontinuation is resumed according to the Trogarzo® Prescribing Information. For re-enrolling subjects, the inclusion criteria for stable a Trogarzo®-containing ARV regimen is satisfied with a loading dose of 2000mg IVI and at least one maintenance dose of 800mg IVI given according to Trogarzo® labeling prior to Day 1 enrollment. (Section 3.1 Overall Design)

Additionally with regard to data collection, Protocol v7.0 states:

PK visits between Baseline and Day 29 will not be required for HIV-infected subjects participating in the IM portion of TMB-302 who have re-enrolled after receiving a 2000mg loading dose and one 800 mg dose of Trogarzo® by IVI prior to study re-enrollment since these PK samples will already have been collected during initial study participation. (Table 1 Schedule of Events for IM Group (HIV-Infected and HIV-Uninfected Subjects)

For the purposes of analysis:

1. Subjects who re-enroll will be assigned a new subject ID, and all data will be collected where possible during the second enrollment, with the exception of PK as described above.
2. While all collected data will be submitted for review as part of the CDISC data package:
  - a. PK data for re-enrolled subjects will be combined such that data collected on Day 1 – Day 29 from the first enrollment and data collected after Day 29 from the second enrollment provide one linear set of results with no overlapping. No data collected after Day 29 from the first enrollment will be included in the analyses of the re-enrolled subjects.
  - b. For all data other than PK, only data collected during the second enrollment will be presented in the analyses.

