### **9.5.1 Adverse Events**

The incidence (n and %) of AEs, SAEs, and early termination of experimental study drug administration or study participation due to an AE will be presented. Additionally, AEs will be tabulated according to severity and relatedness categories as reported by the investigator. AEs will be presented in tables organized alphabetically by Preferred Term within SOC. Each subject will be counted only once for each AE reporting level.

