## **4. Statistical Analysis**

### **4.1. Subject Disposition**

The number of subjects in the ITT and SAF Populations will be tabulated.

Study completion data will be summarized for all enrolled subjects. The number and percent of subjects who complete treatment; discontinue study medication prematurely; or discontinue the study prematurely will be tabulated. The primary reason for premature discontinuation of study medication and/or discontinuation from study participation will be tabulated. Any additional reason(s) for premature discontinuation of study medication will also be tabulated. A listing of all enrolled subjects will be provided.

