##### **4.3.1. Extent of Study Drug Exposure**

Summary statistics will be presented for the cumulative dose (mg) and duration of treatment received by the subjects in the SAF Population. Duration of treatment will be represented as number of days from first dose of study drug. Corresponding listings will also be generated for study drug administration.

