##### **4.3.2. AEs**

All AEs will be coded using MedDRA dictionary version 22.0. The use of another version will not be considered a violation of the SAP, nor require an amendment to the plan. All summary tables will be based on coded preferred terms (PTs), instead of verbatim terms. The categories and definitions of severity and causal relationship for

all AEs, including the criteria for which an AE is to be classified as “serious,” are as described in the protocol (Section 8).

A treatment-emergent AE (TEAE) is defined as any event not present before exposure to study drug or any event already present that worsens in either intensity or frequency following exposure to study drug. All AEs entered on the Adverse Events eCRF will be analyzed as TEAEs. A TEAE with missing severity or relationship will be considered severe or related, respectively.

The overall incidence of TEAEs will be summarized for all subjects in the SAF Population. The number and percentage of subjects having the following will be tabulated:

- TEAE
- Serious TEAE
- TEAE leading to discontinuation
- TEAE with outcome of death
- Suspected Adverse Reaction
- Severe (Grade 3 or 4) TEAE
- Class C TEAE per the Centers for Disease Control and Prevention (CDC) Classification System for HIV Infection

The overall incidence of TEAEs will also be summarized by System Organ Class (SOC), and by SOC and PT. The number and percentage of subjects reporting an event, as well as the number of events reported by the subjects will be tabulated. The incidence of serious TEAEs and TEAEs leading to study discontinuation (if any) will be summarized in the same manner. If there are multiple occurrences of the same TEAE within any SOC or PT for the same subject, only the first occurrence will be counted.

The incidence of TEAEs by severity/grade (Mild, Moderate, Severe, or Potentially life-threatening, Death) and by relationship to study drug (Suspected Adverse Reaction or Unrelated), and the incidence of serious AEs (SAEs) by relationship to study drug, will also be summarized.

All other AEs will be classified as non-TEAEs and identified in listings only. Serious TEAEs, TEAEs leading to study discontinuation, and TEAEs with an outcome of death will be presented in separate listings, if needed.

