**Listing 16.2.7.1**  
**Treatment Emergent Adverse Events [1]**

Group	Subject ID	System Organ Class	Preferred Term [2]	Adverse Event Verbatim			Start Date (Study Day)	Stop Date (Study Day)	Period [3]	Grade [4]	Sev./ SAE	Action Taken [5]	Caus. [6]	Action Taken [7]	Outcm. [8]	CDC AIDS-Defining Cond. [9]
				XXXXXXX	YYYY-MM-DD (XX)	YYYY-MM-DD (XX)										
IM HIV-infected	XX-XXX	XXXXXXXXXXXX	XXXXXXXXXX	XXXXXXXXXX	YYYY-MM-DD (XX)	YYYY-MM-DD (XX)	XXXX	X	N/Y		X	X	X	X	X	X
IM HIV-uninfected	XX-XXX	XXXXXXXXXXXX	XXXXXXXXXX	XXXXXXXXXX	YYYY-MM-DD (XX)	YYYY-MM-DD (XX)	XXXX	X	N/Y		X	X	X	X	X	X
		XXXXXXXXXXXX	XXXXXXXXXX	XXXXXXXXXX	YYYY-MM-DD (XX)	YYYY-MM-DD (XX)	XXXX	X	N/Y		X	X	X	X	X	X

[1] Adverse events occurring on or after the date of first dose of study medication.

[2] Adverse events are coded using MedDRA Version 22.0.

[3] Period represents the timeframe when the adverse event STARTED.

[4] Severity/Grade: 1=Mild, 2=Moderate, 3=Severe, 4=Potentially Life Threatening, 5=Death.

[5] Causality: 0=Unrelated, 4=Suspected Adverse Reaction.

[6] Action Taken: 0=None, 1=Medication Given, 2=Non-Medication Therapy, 3=Suspended Study Drug, 4=Permanently Discontinued Study Drug, 99=Other.

[7] Outcome: 1=Resolved, 2=Resolved w/sequelae, 3=Ongoing, 4=Worsened, 5=Death, 7=Chronic/Stable, 98=Unknown.

*Notes to programmer: Confirm that footnotes match final version of CRF and coding used in data.*

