**Table 14.1.1**  
**Subject Disposition**

	IM HIV Infected (N=XX) n (%)	IM HIV Uninfected (N=XX) n (%)	Total (N=XX) n (%)
Study Populations			
Screened	n	n	n
Intent-to-Treat (ITT) [1]	n (xx.x%)	n (xx.x%)	n (xx.x%)
Safety (SAF) [2]	n (xx.x%)	n (xx.x%)	n (xx.x%)
Study Completion Status			
Completed Study Per Protocol	n (xx.x%)	n (xx.x%)	n (xx.x%)
Ongoing in Study	n (xx.x%)	n (xx.x%)	n (xx.x%)
Discontinued Study Prematurely	n (xx.x%)	n (xx.x%)	n (xx.x%)
Treatment Completion Status			
Completed Treatment Per Protocol	n (xx.x%)	n (xx.x%)	n (xx.x%)
Continuing Treatment	n (xx.x%)	n (xx.x%)	n (xx.x%)
Discontinued Treatment Prematurely	n (xx.x%)	n (xx.x%)	n (xx.x%)

N = All subjects enrolled (displayed according to assigned treatment), and denominator for percentage calculations.

[1] ITT Population consists of all subjects enrolled into the study.

[2] SAF Population consists of subjects receiving at least one partial dose of study drug.

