**Table 14.3.2.1**  
**Abnormal Laboratory Results by DAIDS Toxicity Grade [1] and Route of Administration**  
**Safety Population - IM HIV Infected Group**

Test/Route of Administration [2]	IM HIV Infected (N=XX)				
	Grade 0 n (%)	Grade 1 n (%)	Grade 2 n (%)	Grade 3 n (%)	Grade 4 n (%)
Analyte 1					
IV Infusion (Day 1 - Day 29)	n (xx.x%)	n (xx.x%)	n (xx.x%)	n (xx.x%)	n (xx.x%)
IM Injection (Day 30 - Day 85)	n (xx.x%)	n (xx.x%)	n (xx.x%)	n (xx.x%)	n (xx.x%)
Follow-up (Day 86 - Day 99)	n (xx.x%)	n (xx.x%)	n (xx.x%)	n (xx.x%)	n (xx.x%)
Analyte 2					
IV Infusion (Day 1 - Day 29)	n (xx.x%)	n (xx.x%)	n (xx.x%)	n (xx.x%)	n (xx.x%)
IM Injection (Day 30 - Day 85)	n (xx.x%)	n (xx.x%)	n (xx.x%)	n (xx.x%)	n (xx.x%)
Follow-up (Day 86 - Day 99)	n (xx.x%)	n (xx.x%)	n (xx.x%)	n (xx.x%)	n (xx.x%)

N= All Subjects enrolled (displayed according to assigned treatment) and denominator for percentage calculations.

[1] If a subject reported more than one abnormal result for a given analyte at any point during the study, only the result with the highest grade is counted.

[2] Indicates the route of administration by which the subject was receiving study drug at the time the laboratory result was recorded.

*Note to programmer: 1) Use TRTA to create the rows within each analyte. 2) For each value of PARAMCD select the highest grade for each subject, regardless of visit or period. 3) Count the frequency by analyte, period, and grade.*  
*Only include analytes with abnormal results in the data in this table.*

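### IM SAP addendum item 2b, as written, leaves first-enrolment safety and exposure data of re-enrolled IM subjects, and very likely their discontinuation, out of the planned tables

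*SAP*

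**What the plan says.** The IM SAP Addendum deals with HIV-infected IM subjects who could not keep to the IM dosing schedule for reasons unrelated to the study, were discontinued, and enrolled again under a new subject ID. Item 2a joins their PK data: Day 1 to Day 29 from the first enrolment, later days from the second. Item 2b covers everything else: "For all data other than PK, only data collected during the second enrollment will be presented in the analyses". The stated destination for all collected data, including what the analyses leave out, is the CDISC submission package.

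Elsewhere the IM SAP describes its tables without any such limit:

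- Adverse events (Section 4.3.2): "The overall incidence of TEAEs will be summarized for all subjects in the SAF Population".
- Exposure (Section 4.3.1): "Summary statistics will be presented for the cumulative dose (mg) and duration of treatment received by the subjects in the SAF Population".
- Disposition (Section 4.1): "Study completion data will be summarized for all enrolled subjects". The footnote to mock Table 14.1.1 reads "N = All subjects enrolled (displayed according to assigned treatment), and denominator for percentage calculations".
- Laboratory grades (mock Table 14.3.2.1, footnote 1): "If a subject reported more than one abnormal result for a given analyte at any point during the study", only the highest grade is counted.

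The protocol also has an analysis rule for re-enrolled subjects, in Sections 3.6, 6.3 and 9.7. It concerns PK only.

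**The concern.** Safety of IM injection is a primary objective (IM SAP Section 2.2.1), and the IM set is about 20 subjects. Re-enrolment presupposes an earlier discontinuation, and by then a subject may already have had IM injections. The authors evidently foresaw this, because item 2a deals expressly with first-enrolment data after Day 29, the day IM dosing starts. Under item 2b, an adverse event after one of those injections, a Grade 3 laboratory value in that period, and the doses themselves would appear in no safety or exposure table.

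Two side effects follow.

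- Item 2a uses the first-enrolment infusions as the PK reference. Under 2b, those same infusions are missing from the exposure table and any event after them is missing from the adverse event tables.
- Listing 16.2.7.1 defines treatment-emergent events as "Adverse events occurring on or after the date of first dose of study medication". If only second-enrolment data count, an event that began after a first-enrolment injection and continued unchanged could be taken as pre-existing.

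**Working it through.** The plan gives no figure for this point, so there is none to reproduce. The check has a textual part and an illustration of size.

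**Text.** Item 2b covers all non-PK data. Adverse events (Tables 14.3.1.x), worst laboratory grade (14.3.2.1), cumulative dose and duration (14.3.5.1), and disposition with reasons (14.1.1, 14.1.2) are all non-PK. Nothing in the addendum exempts them. Set beside Sections 4.1, 4.3.1 and 4.3.2 and the footnote to Table 14.3.2.1, the rule would make the table descriptions untrue for a re-enrolled subject: dose received would not be all the dose received, and the highest grade in the study would be the highest grade in the second enrolment.

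**Inputs.** 20 planned IM subjects (IM SAP Section 3.1); 4 IM doses per full course, after 2 infusions (Section 2.1); 800 mg per dose (Section 2.3); one further infusion at Day 85 for HIV-infected subjects. The number of re-enrolled subjects, k, and the number of first-enrolment IM doses each, d, are not in the documents. I take k = 1 to 5 and d up to 3 as assumptions; a subject with four IM doses has finished the IM course. If k or d is zero, no IM dose is omitted.

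**Untabulated IM doses.** Planned and tabulated: 20 × 4 = 80. Omitted share = kd / (80 + kd).

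- k = 1, d = 1: 1/81 = 1.2%
- k = 3, d = 2: 6/86 = 7.0%
- k = 5, d = 3: 15/95 = 15.8%

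This ignores replacement subjects (Section 2.4.4), who would enlarge the denominator and lower the shares.

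**Mean cumulative dose, HIV-infected column of Table 14.3.5.1.** A completed enrolment is 2 + 4 + 1 = 7 doses, 7 × 800 = 5600 mg. A first enrolment with both infusions adds 1600 mg plus 800 mg per IM dose, so 1600 mg (d = 0) to 4000 mg (d = 3). I assume that everyone else completes. The number of HIV-infected subjects is not stated, so I take 20 and 10.

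- One re-enrolled of 20 infected: shown 20 × 5600 = 112,000 mg. Understated by 1600/113,600 = 1.4% to 4000/116,000 = 3.4%.
- One re-enrolled of 10 infected: shown 56,000 mg. Understated by 1600/57,600 = 2.8% to 4000/60,000 = 6.7%.
- Extreme case, five re-enrolled with d = 3: 20,000/132,000 = 15% (20 infected) or 20,000/76,000 = 26% (10 infected).

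**Discontinuations.** If the first enrolment is dropped from Table 14.1.1, each re-enrolled subject removes one premature discontinuation: 1/20 = 5%, 3/20 = 15%, 5/20 = 25%.

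**Duration.** No figure is given. Section 4.3.1 counts days from first dose but names no end point and has no rule for the gap between enrolments.

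**The case against.** The strongest reply is that the general sections were written before re-enrolment existed, and that the addendum is the later, specific rule meant to adapt them. The laboratory footnote says which of several results to count. It does not promise to pool two enrolments held under two subject IDs. The protocol is silent on non-PK data, and silence is not contradiction. This stands in part: item 2b can be read as a deliberate override, and the protocol does not forbid it. But the addendum does not say that it redefines the safety population or the content of these tables, and nothing in the protocol supports dropping safety data.

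Disposition is less clear-cut. Section 4.1, the Table 14.1.1 footnote and general programming note 4 for tables, which wants every subject accounted for, could lead a programmer to keep the first enrolment as a discontinued record. A reader might infer that the discontinuation is always lost. The text makes that very likely, not certain.

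A reader might also infer that safety information is being suppressed, or that event rates will be biased downwards. The documents do not support either.

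- All data go into the CDISC package, and listing note 7 asks for all applicable data.
- SAE reporting and DMC review are unchanged (Protocol Sections 8.6 and 8.8).
- Re-enrolment is for reasons outside the study, subjects with dose-limiting toxicity follow a separate path (Protocol Section 4.3), and eligibility must be met again.

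Finally, re-enrolling subjects are exempt from end-of-study procedures and 28-day follow-up (Protocol Sections 6.4 and 6.5), so their first-enrolment safety data may be truncated. That is a reason to label the data, not to omit them.

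**Conclusion.** The point holds as a conflict in the planned tables and should be fixed. Followed literally, item 2b omits adverse events, laboratory grades and doses that occurred on study from the tables serving a primary safety objective, and very probably the discontinuation as well. It is a wrong rule rather than a missing detail.

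Its size is unknown and may be zero. Under the stated assumptions, 1.2% to 15.8% of IM doses would go untabulated. With one re-enrolled subject, the HIV-infected mean cumulative dose would be understated by about 1.4% to 3.4% (20 infected) or 2.8% to 6.7% (10 infected). A reader could compute a larger share for one person, 1600/7200 = 22% to 4000/9600 = 42% of that person's on-study dose, but those figures do not describe the table.

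The finding is incompleteness; the direction of any effect on event rates is not established. Any gap in planned injection-site or anti-drug-antibody outputs is a separate matter that item 2b does not cause.

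**What to change.** Restrict item 2b to by-visit change-from-baseline summaries, viral load and questionnaires, and keep item 2a for PK. Then add to the addendum:

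- The adverse event, SAE, worst-grade laboratory and exposure tables include both enrolments, linked by USUBJID. Each person counts once per event level, in line with Protocol Section 9.5.1 ("Each subject will be counted only once for each AE reporting level"), and events are assigned to the administration route in use at onset.
- One consistent rule covers events recorded between enrolments, so that no event is defined as treatment-emergent and then left out of the treatment-emergent tables.
- Treatment duration is defined explicitly for re-enrolled subjects, including its end point and how the gap is handled.
- Tables 14.1.1 and 14.1.2 gain a row, *Discontinued first enrolment and re-enrolled*, with reasons.
- Second-enrolment-only safety results are shown as a sensitivity analysis.
- Footnotes state that re-enrolled subjects may contribute more than four IM doses and that their first-enrolment follow-up may be shorter than 28 days.

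The cost is SAP wording and some programming. The data are already collected, and IM SAP Section 2.4.1 already plans a USUBJID common to all enrolments. The downside is that re-enrolled subjects bring more doses and time at risk into person-level percentages; the sensitivity analysis and footnotes make that visible. A footnoted supplementary summary of first-enrolment events, doses and discontinuations would be a lighter alternative, but the main safety tables would remain incomplete.

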**Notes Applicable to All Listings**

General Programming Notes:

1. There are a few listings that might fit as they are or might have to be split once we see the output with actual data.
2. All listings should start with and be sorted by Group (Sentinel or IM), Subject ID (concatenation of site number and Subject number), and visit date as appropriate.
3. If columns with specific text should be widened due to the amount of text, it is up to the programmer's discretion. However, please keep to the industry standard margin of 1 inch on bottom and sides and 1.25 inches on the top. Font is Courier New 8 point.
4. For all dates used, character format dates to capture partial dates. Use dashes where a month or day is missing. If entire date is missing just leave blank. i.e., - JAN2011 or 01-2011.
5. If a programming note appears on the mock listing indicating that the footnote should appear only on the first page, this means the first page of output contains all footnotes and ONLY footnotes. All subsequent pages contain data with one footnote that says "Refer to page 1 for footnotes".
6. Some of the mock tables display numbers rather than x's. The numbers are meaningless and are for example only. Where visit names are displayed in tables, these are examples as well. Correct visit names for the TMB-302 study should be displayed in the actual output.
7. Each listing should include all applicable data, even if only a subset of the full set of treatment groups is displayed in the mocks.
8. Sort each listing by Group and then Subject ID where applicable.
9. Add "Period" to any applicable listing as the data dictates. Some listings below have period added with example values.

**Listing 16.2.1.1**  
**Subject Disposition**

---

Group	Subject ID	Screened	ITT	SAF
			Population [1]	Population [2]
IM HIV Infected	XX-XXX	YES	YES	YES
	XX-XXX	YES	YES	YES
IM HIV Uninfected	XX-XXX	YES	YES	YES
	XX-XXX	YES	YES	YES

---

[1] Intent-to-Treat (ITT) Population consists of all Subjects enrolled into the study.  
[2] Safety (SAF) Population consists of Subjects receiving at least one partial dose of study drug.

**Listing 16.2.1.2  
Discontinuation**

Group	Subject ID	Study Discontinuation Date	Date of Last Study Treatment	Completed Study Treatment	Reason for Treatment Discontinuation	Completed Study	Reason for Study Discontinuation	Death Date
IM HIV Infected	XX-XXX	YYYY-MM-DD	YYYY-MM-DD	YES/NO	XXXXXXXXXXXX	YES/NO	XXXXXXXXXXXX	YYYY-MM-DD
IM HIV Uninfected	XX-XXX	YYYY-MM-DD	YYYY-MM-DD	YES/NO	XXXXXXXXXXXX	YES/NO	XXXXXXXXXXXX	YYYY-MM-DD

Westat (Created on DDMMYYYY)  
S:\TMB302\DA\_IM \SAS\L\_DISCRSN.SAS

**Listing 16.2.2.1  
Protocol Violations**

Group	Subject ID	Visit	Start Date	Stop Date	Violation Code	Details of Violation
IM HIV Infected	XX-XXX	XXXXX	YYYY-MM-DD	YYYY-MM-DD	XXX	XXXXXXXXXX
IM HIV Uninfected	XX-XXX	XXXXX	YYYY-MM-DD	YYYY-MM-DD	XXX	XXXXXXXXXX

Westat (Created on DDMMMYYYY)  
S:\TMB302\DA\_IM \SAS\L\_PROTVI0S.SAS

**Listing 16.2.2.2  
Protocol Deviations**

---

Group	Subject ID	Visit	Start Date	Stop Date	Deviation Code	Details of Deviation	Approval Obtained	Date of Approval
IM HIV Infected	XX-XXX	XXXXXX	YYYY-MM-DD	YYYY-MM-DD	XXX	XXXXXXXXXX	Yes/No	YYYY-MM-DD
IM HIV Uninfected	XX-XXX	XXXXXX	YYYY-MM-DD	YYYY-MM-DD	XXX	XXXXXXXXXX	Yes/No	YYYY-MM-DD

---

Westat (Created on DDMMMYYYY)  
S:\TMB302\DA\_IM \SAS\L\_PROTDEV.SAS

